#### 5.3. Withdrawal criteria

- A subject may be withdrawn from therapy
- On account of development of an intolerable adverse event.
- A female subject will be withdrawn if she gets pregnant during the course of the study.

- A subject may also be withdrawn based on the discretion of the investigator for any reason, if it is felt that his/her further continuation in the trial will adversely affect him/her, or, in the interests of the study.
- Subject will be considered to have withdrawn from the study if the subject is lost to follow-up, died, is no longer being followed at the investigator's discretion
- A subject may also be withdrawn if the subject volunteers to do so. The reason for discontinuation should be documented and all serious adverse events should be reported to the Medical Monitor from [name].

All the efficacy and safety parameters are to be assessed and all applicable activities of visit 4 will be conducted at the time of discontinuation of the study.

The primary reason for withdrawing from the study will be clearly documented in the subject's medical record and recorded on the CRF.

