Patients will continue to provide their daily assessments, their weekly assessments, and their use of rescue medicine and any other laxatives, suppositories, or enemas up to 2 week or EOT.

A list of these assessments and the visits when they are performed is provided in the Schedule of Evaluations.

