## 7.2. Early Termination of the Study

Sponsor reserves right to discontinue the study at any time. Principal Investigator reserves the right to discontinue the study for safety reasons at any time. Independent / Institutional Ethics Committee (IEC) may ask to terminate the study, if there are major violations of ethical considerations or due to any serious adverse event(s). Reason(s) for termination of study will be provided to the subjects.

If a subject experiences any AE/SAE or worsening of the existing condition he/she can visit the site for an unscheduled visit. Subjects who withdraw from the study will be requested to attend an early termination visit, where Visit 4 (end of trial visit) procedures will be performed.

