#### • Permitted concomitant medications:

Concomitant medicines are defined as any medicines taken during the treatment period (i.e., between the date of the first dose of study drug in the treatment period and the date of the last dose of study drug in the treatment period, inclusive). Any medicines started after the date of last dose of study drug will not be considered concomitant medicines. Both prior and concomitant medicine use will be summarized by the number and proportion of patients in each treatment group receiving each medicine within each therapeutic class. Concomitant medicine will be summarized for the treatment period using the Safety Population.

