All SAE reports shall be submitted to the DCGI as per – table 5 of schedule III of New Drugs and Clinical Trials Rules 2019 G.S.R. 227(E), in accordance with the format and checklist (based on the event). The sponsor will submit all SAE report to CDSCO via SUGAM portal as per table 5 of schedule III of New Drugs and Clinical Trials Rules 2019 G.S.R. 227(E). The sponsor or its representative shall submit all SAE reports to CDSCO as per table 5 of schedule III of New Drugs and Clinical Trials Rules 2019 G.S.R. 227(E). The SAE reports will be submitted with proper binding, indexing and page number.

Sponsor shall share the due analysis report with all other participating Investigator(s) / study site team(s) and same has to be notified by site team(s) to their respective IECs

All adverse events, independent of relationship to study drug, must be reported starting from time of first administration of study drug until end of study or early termination. Subjects will be followed-up for adverse events until complete resolution.

All SAEs will be followed until resolution, stabilisation, until the event is otherwise explained, or the patient is lost to follow-up.

A event which occurs before administration of study drug/procedure (e.g. during screening/as a result of screening, after signing the ICF and before administration of the study drug, during check-in/after check-in and before administration of the study drug)

will not be considered as adverse event for the investigational product and hence it will not be reportable as adverse event for the investigational product to the applicable regulatory authorities (e.g. DCGI, etc.).

If there is any change in the Pharmacovigilance regulation by the DCGI (licensing authority) in regard to the SAE reporting, the timelines for SAE reporting, the concerned authorities/ personnel to whom the SAE's has to be reported then the applicable Pharmacovigilance regulations will be followed by Investigator / Sponsor. The investigator / Sponsor will comply to the changes in the Pharmacovigilance regulations (SAE reporting and timelines for SAE reporting), by the DCGI (licensing authority) on their responsibilities. The investigator will cooperate with the sponsor in complying to the change in the Pharmacovigilance regulation (SAE reporting and timelines for SAE reporting), as applicable.

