## 13.2. Sample Size Estimation

A total of 150 patients with chronic constipation will be enrolled in the study.

Assuming a significance level of 2.5% and a power of 95%, we require 60 completed subjects per treatment group (a total of 120 subjects in study) to prove superiority of Elobixibat.

Assuming ~20% drop-out rates, 150 subjects will be randomized in this study with 1:1 ratio (75 subjects per each arm) to Elobixibat 5mg vs Placebo.

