## 13.3. Statistical Analysis

A Statistical Analysis Plan (SAP) will be prepared as a separate document and finalized before database lock. Any deviation from the original statistical plan will be described and justified in the final report, as appropriate. The procedure for accounting for missing, unused and spurious data will be included in the Statistical Analysis Plan. All statistical analysis will be conducted using SAS®, Version 9.4 or higher.

The accepted per-protocol (PP) population used for evaluation includes all randomized subjects who meet all inclusion/exclusion criteria, dosed a pre-specified proportion of the scheduled doses of the assigned product for the specified duration of the study, do not miss a pre-specified number of scheduled doses for more than pre-specified number of days, and complete the evaluation within the designated visit window with no protocol violations that would affect the treatment evaluation. The protocol should specify how compliance will be verified, (e.g., by the use of subject diaries).

The mITT and safety populations include all randomized subjects who use at least one dose of product.

Subjects who are discontinued early from the study due to lack of treatment effect should be included in the PP population. Subjects whose condition worsens and who require alternate or supplemental therapy, excluding pre-specified rescue therapies, for the treatment of constipation during the treatment phase of the study should be discontinued, included in the mITT and PP population analysis, and provided with effective treatment. Subjects discontinued early for other reasons should be excluded from the PP population but included in the mITT population. The protocol should clearly state how missing data will be handled in the statistical analyses and provide appropriate justification for the method chosen.

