## 13.3.1. Efficacy analysis

The primary efficacy parameter is Change from baseline in weekly frequency of Spontaneous Bowel Movement (SBMs).

The primary efficacy analysis the proportion of 2-week SBM Overall Responders will be compared to the proportion in the placebo group using the CMH test.

The secondary efficacy parameters are:

- 1. Proportion of patients with complete spontaneous bowel movement (CSBM)
- 2. Proportion of patients with a SBM within 24 h after the first dose of study drug
- 3. Median time to first SBM
- 4. Change from baseline in Stool consistency using Bristol Stool Form Scale (BSFS)
- 5. Change from Baseline in Weekly Degree of Straining of SBMs
- 6. Change from Baseline in Weekly Abdominal Bloating Score
- 7. Change from Baseline in Weekly Abdominal Discomfort Score

For each of the above secondary efficacy parameters, Elobixibat dose group will be compared to the placebo group using an analysis of covariance (ANCOVA) model with fixed effect terms for treatment group and the patient's corresponding baseline value of the parameter as a covariate. The overall type I family-wise error rate for testing the primary and secondary efficacy parameters will be controlled at the 0.05 significance level using the following five-step serial gatekeeping multiple comparisons procedure (MCP).

All hypothesis tests will be two-sided.

The first step will test the primary efficacy parameter for the Elobixibat 5mg dose group at the 0.05 significance level

The second step will test the primary efficacy parameter for the 5mg Elobixibat dose group and the first five secondary parameters (i.e., SBM, CSBM, stool consistency, severity of straining, and constipation severity).

The third step will test the last two secondary parameters (i.e., bloating, abdominal discomfort) for the Elobixibat 5mg dose group. The two individual hypotheses within this step will be tested using an overall type I error rate of 0.05 by means of a Hochberg procedure to control for multiple parameters.

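### The protocol does not separate stopping study drug from leaving the study, so no stated route keeps the diary going to Day 14 in patients whom the mITT analysis still includes

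*Protocol*

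**What the plan says.** Section 5.3 starts from withdrawal from therapy. It then lists intolerable adverse events, pregnancy, investigator discretion, loss to follow-up or death, and the patient's own choice. One instruction follows for all of them: efficacy and safety are assessed and "all applicable activities of visit 4 will be conducted at the time of discontinuation of the study".

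The related passages are:

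- **Section 7.2** (and the synopsis): "Subjects who withdraw from the study will be requested to attend an early termination visit". Visit 4 procedures are done there, and 7.2 labels Visit 4 the end-of-trial visit.
- **Section 4.1**, treatment period: patients report daily and weekly assessments and "their use of rescue medicine and any other laxatives, suppositories, or enemas up to 2 week or EOT". The abbreviation list expands EOT as End-of-Trial.
- **Section 9.7**, pregnancy: a patient taken off study treatment for pregnancy has early termination assessments as soon as possible.
- **Section 9.7**, adverse events: these "must be reported starting from time of first administration of study drug until end of study or early termination". Section 9.6 ends reporting at a Visit 5 or early termination visit, although the schedule stops at Visit 4.
- **Section 13.3**: mITT is every randomized patient with at least one dose. "Subjects discontinued early for other reasons should be excluded from the PP population but included in the mITT population". Patients who stop for lack of effect or worsening stay in the PP population as well.
- **Sections 4.3.1 and 13.3.1**: the primary parameter is the change in weekly SBM frequency, which 4.3.1 times from baseline to two weeks.

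**The concern.** The protocol commits to analysing patients whose remaining outcome it makes no provision to collect. A patient who stops tablets on Day 4 and has Visit 4 brought forward has a diary of about four days and nothing for Week 2, yet still counts in the mITT comparison of a two-week endpoint.

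Reasons for stopping may differ by arm. The product information in Section 1.2 lists diarrhoea at 14.4% and abdominal pain at 23.2%, and Section 13.3 itself foresees stops for lack of effect. If they do differ, the unobserved days are not a random subset, and the treatment comparison then rests partly on how they are filled in. The SAP can choose that method, but it cannot restore diary days that nobody asked the patient to record.

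New adverse events, and new constipation treatment begun between the stop and Day 14, would also go unrecorded.

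**Working it through.** **1. Is there any route for staying in the study off drug?** Reading the sections together:

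- 5.3 mentions both therapy and study withdrawal, with one procedure.
- 7.2 calls the visit that results end-of-trial.
- 4.1 ends the diary at two weeks or end of trial.
- 9.7 ties a treatment stop to the early termination visit explicitly, for pregnancy only.
- 8.2 foresees reducing, suspending or discontinuing the drug for symptoms, and says nothing about follow-up afterwards.

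No section tells a patient who has stopped drug to keep the diary or attend on Day 14.

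**2. The plan's own figure.** Inputs from Section 13.2: 60 completers per arm, drop-out about 20%, 1:1 allocation.

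- Randomized per arm = 60 / (1 − 0.20) = 75, total 150. This matches the protocol.
- Drop-outs allowed for = 0.20 × 75 = 15 per arm, 30 in total.

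The inflation protects the number of completers. It does nothing about who is missing.

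**3. Why 30 is a ceiling.** It is the whole planned allowance, including patients lost to follow-up or refusing further contact, whom no wording can recover. What is missing is the complete two-week value: a patient leaving after Day 10 still has all of Week 1 and Days 8 to 10, that is 3 of 7 Week 2 days.

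**4. Can the direction of bias be fixed?** Two illustrations, both with assumed figures:

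- *Last on-drug rate carried forward.* Active patients stopping for diarrhoea carry +8 SBM/week when their change after stopping would be +1. Shift in the active mean = (stoppers / 75) × 7: 4 stoppers give 0.37 and 8 give 0.75 SBM/week, upward. The label incidence implies 0.144 × 75 = 10.8 diarrhoea cases per 75, and those are cases, not stops.
- *Recorded Week 2 count used as it stands.* Patients at 7 SBM/week leaving after Day 10 show about 3 instead of 7. Shift = (stoppers / 75) × (−4): 4 give −0.21 and 8 give −0.43, downward.

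The sign changes with the handling rule. Section 13.3.1 also describes a responder comparison by CMH test for the primary analysis, so a shift in a mean does not translate directly.

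**5. What would follow-up off drug do to power?** Section 13.2 states "Assuming a significance level of 2.5% and a power of 95%, we require 60 completed subjects per treatment group" but no effect size, so one must be back-solved. With two-sided 0.05 (equivalently one-sided 0.025), d = (1.960 + 1.645) × √(2/60) = 0.658. Suppose all 20% are drug stoppers followed to Day 14, and they retain a fraction r of the effect. The diluted effect is 0.658 × (0.8 + 0.2r). Power with 75 per arm, by normal approximation with unchanged SD:

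| r | diluted d | power |
|---|---|---|
| 0 | 0.527 | 89.7% |
| 0.5 | 0.592 | 95.2% |
| 1 | 0.658 | 98.1% |

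With 10% stoppers the range is 95.2% to 98.1%. This is an illustration for a comparison of means only.

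**The case against.** The strongest reply is that the protocol never says that stopping drug means leaving the study. The instruction in 5.3 refers to discontinuing the study, 7.2 addresses patients who withdraw from the study, and the diary ends at end of trial, not at last dose. That is correct. A reader might infer an outright rule that stopping ends participation, but it is explicit only for pregnancy. What stands is the gap: the two events share one procedure and no alternative is written, so sites may well treat them as one.

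Four further inferences go too far:

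- *Adverse event collection ends at the stop.* Only the reporting of new events ends. Section 9.7 follows existing adverse events to resolution, and 7.1.4 and 9.6.1 follow clinical findings and serious events until resolved or stable.
- *A laxative begun after stopping is excluded by rule.* Section 8.4 says "Any medicines started after the date of last dose of study drug will not be considered concomitant medicines", but that defines what is summarized as concomitant. Such a laxative goes unrecorded because the diary may have ended.
- *The bias favours active.* The documents shown give no handling rule, and the two illustrations point in opposite directions.
- *The broad investigator grounds in 5.3 should be cut.* They decide who is withdrawn, not what is collected afterwards, and the point does not need them changed.

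It can also be argued that off-drug follow-up serves one estimand among several. Section 13.3 has worsening patients given effective treatment, and movements within 24 hours of laxative use are not SBMs, so later diary days do not measure quite the same thing. That stands as a reason for an analysis rule. It is not a reason to leave the days unrecorded, since recorded days can be set aside and unrecorded ones cannot be recovered.

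**Conclusion.** The point holds as a gap in data collection. The protocol does not separate stopping drug from leaving the study, brings Visit 4 forward for both, and offers no stated way to complete the two-week diary off drug, while keeping these patients in mITT.

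The reach is at most 30 of 150 patients (15 per arm), assuming the planned 20% drop-out occurs and every drop-out leaves before the endpoint is complete. The number the fix could recover is smaller by those who refuse or are lost. Bias is possible if reasons for stopping differ by arm; its sign and size are not established. This is worth correcting because it is cheap, and because no later analysis decision can make up for it. It does not by itself invalidate the trial.

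**What to change.** In Sections 4.1, 5.3 and 7.2, distinguish a patient who stops study drug from one who withdraws consent for further data or cannot be reached. Then:

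- Ask patients who stop drug but agree to further data collection to keep the diary, including rescue and other laxative use, to Day 14 and to attend Visit 4 as scheduled.
- Record new adverse events, and new laxatives or other constipation treatment, to Day 14 or last contact. Align 9.6 and 9.7 accordingly, and correct the reference in 9.6 to a Visit 5 that the schedule does not contain.
- State how diary days after other laxative use enter the analysis.

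Leave the grounds for stopping drug or withdrawing a patient as they are, together with the assessments required on learning of a pregnancy.

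The cost is protocol wording and site training, since the diary and Visit 4 already exist. The burden is about 10 further diary days for a patient who stops on Day 4 (Days 5 to 14), and fewer for later stops. It falls on a minority of patients, some of whom will decline.

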#### **5.4.** Rescue Medication

Rescue Medicine, dispensed to patients, is a choice of 5-mg bisacodyl Capsules or 10-mg bisacodyl suppositories.

During the Pretreatment and Treatment Periods, patients could use Rescue Medicine when at least 72 hours had passed since their previous bowel movement or when their symptoms became intolerable.

A bowel movement will not be recorded in the analysis of efficacy if it occurs within 24 hour after the last administration of a rescue medication. Data set prepared should include daily rescue medication used for each individual who used the rescue medication at any point during the study.

## 5.5. Planned Sample Size and Number of Study Centers

A total of 150 subjects will be enrolled in this study from approximately 10-15 study centres across India.

## 6. STUDY ASSESSMENTS

# **6.1.** Efficacy assessments

 Change from baseline in weekly frequency of Spontaneous Bowel Movement

(SBMs)

- 2. Proportion of patients with complete spontaneous bowel movement (CSBM)
- 3. Proportion of patients with a SBM within 24 hour after the first dose of study drug
- 4. Median time to first SBM
- 5. Change from baseline in Stool consistency using Bristol Stool Form Scale (BSFS)
- 6. Change from Baseline in Weekly Degree of Straining of SBMs
- 7. Change from Baseline in Weekly Abdominal Bloating Score
- 8. Change from Baseline in Weekly Abdominal Discomfort Score

## **6.2.** Safety assessments

The safety parameters include AEs, clinical laboratory parameters, vital signs, and ECG parameters. For each safety parameter, the last assessment made before randomization will be used as the baseline parameter.

## **6.3. Efficacy Variables**

#### **6.3.1.** Primary efficacy variables

- Change from baseline in weekly frequency of Spontaneous Bowel Movement (SBMs)
  - SBM is defined as bowel movement occurring in the absence of laxative use or manual disimpaction in last 24 hours
  - Change from baseline in the frequency of SBM per week.

#### **6.3.2.** Secondary Efficacy variables

- 1. Proportion of patients with complete spontaneous bowel movement (CSBM)
  - CSBM is defined as SBM that is associated with a sense of complete evacuation.
  - A CSBM responder is defined as a patient with ≥3 CSBMs per week and an increase of ≥1 CSBM per week from Baseline.

- 2. Proportion of patients with a SBM within 24 h after the first dose of study drug
- 3. Median time to first SBM
  - SBM is defined as a bowel movement that occurred in the absence of a laxative use or manual disimpaction.
  - Baseline value for the number of SBM is defined as the average of the numbers of SBM per week for over the 2-week pretreatment Period.
- 4. Change from baseline in Stool consistency using Bristol Stool Form Scale (BSFS)
- Change from baseline in weekly Stool Consistency using BSFS score, Time
   Frame: From baseline to 2 weeks
- The stool consistency is measured using the seven-point ordinal BSFS score.
- The BSFS classifies human stool into seven types and points them accordingly:
  - o Type 1: Separate hard lumps, like nuts (hard to pass)
  - o Type 2: Sausage-shaped, but lumpy
  - o Type 3: Like a sausage but with cracks on its surface
  - o Type 4: Like a sausage or snake, smooth and soft
  - o Type 5: Soft blobs with clear cut edges (passed easily)
  - o Type 6: Fluffy pieces with ragged edges, a mushy stool
  - Type 7: Watery, no solid pieces, entirely liquid
- Types 1 and 2 indicate constipation, with 3 and 4 represents the ideal stool form (especially the latter), and 5, 6 and 7 tends towards diarrhoea.
- For a given assessment week, the weekly stool consistency is defined as the sum of non-missing stool consistency score for SBMs during that week divided by the number of non-missing stool consistency score for SBMs during that week.
- 5. Change from Baseline in Weekly Degree of Straining of SBMs
- The degree of straining is measured using the five-point ordinal scale (1=Not at all, 2=A little bit, 3=A moderate amount, 4=A great deal, and 5=An extreme amount).
- For a given assessment week, the weekly degree of straining is defined as the sum of non-missing straining score for SBMs during that week divided by the number of non-missing straining score for SBMs during that week.

- 6. Change from Baseline in Weekly Abdominal Bloating Score
- The abdominal pain score is measured using the five-point ordinal scale (1=None, 2=Mild, 3=Moderate, 4=Severe, and 5=Very severe).
- For a given assessment week, the weekly abdominal bloating score is defined as
  the sum of non-missing abdominal bloating score for SBMs during that week
  divided by the number of non-missing abdominal bloating score for SBMs
  during that week.
- 7. Change from Baseline in Weekly Abdominal Discomfort Score
- The abdominal discomfort score is measured using the five-point ordinal scale (1=None, 2=Mild, 3=Moderate, 4=Severe, and 5=Very severe).
- For a given assessment week, the weekly abdominal discomfort score is defined
  as the sum of non-missing abdominal discomfort score for SBMs during that
  week divided by the number of non-missing abdominal discomfort score for
  SBMs during that week.

